13.1.2. Adverse Events (AE)

The incidence of treatment-emergent adverse events, defined as all AEs that occur after the administration of IMP, and their relatedness to experimental treatment will be summarized by treatment group, by system organ class and preferred term, maximum severity, and potential relationship to IMP, SAE, as well as TEAEs with an outcome of death, serious TEAEs, and discontinuations due to TEAEs. These summary tables will be restricted to AEs with date of onset during or up to 14 days after treatment. Separate summary tables will be created for the incidence of AEs over the whole study period.

Adverse events will be coded by System Organ Class (SOC) and Preferred Term (PT) using the Medical Dictionary for Regulatory Activities (MedDRA) dictionary.

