## 1 PROTOCOL SYNOPSIS

Short protocol Title	PanACEA DE lpazolid dose-finding and CO mbination DE velopment (DECODE)								
Full protocol title	A Phase IIb, Open-Label, Randomized Controlled Dose Ranging Multi-Center Trial to Evaluate the Safety, Tolerability, Pharmacokinetics and Exposure-Response Relationship of different doses of Delpazolid in combination with Bedaquiline, Delamanid and Moxifloxacin in Adult Subjects with Newly Diagnosed, Uncomplicated, Smear-Positive, Drug-sensitive Pulmonary Tuberculosis								
Name of IMP	Delpazolid (DZD) 400 mg tablets								
Non-IMP study drugs	Bedaquiline (BDQ), Delamanid (DLM), Moxifloxacin (MXF)								
Indication	Pulmonary Tuberculosis (TB)								
Objectives	Safety and Tolerability Objective:								
	To describe the safety, tolerability and exposure-toxicity relationship of DZD given over 16 weeks, in combination with standard-dose BDQ, DLM and MXF, compared to standard-dose BDQ, DLM and MXF alone								
	Efficacy Objectives:								
	Primary Efficacy Objective :								
	
 
To establish an exposure-response model for DZD, given over 16 weeks in combination with standard-dose BDQ, DLM and MXF, on the change in liquid culture MGIT time to positivity (TTP)
 
								
	Secondary Efficacy Objective:								
	
 
To assess dose and exposure-response relationships for DZD, based on secondary efficacy endpoints, including month-2 culture status in liquid media and on solid media, and time to culture conversion in liquid and on solid media
 
To assess the relative efficacy of increasing DZD doses compared to the background regimen without DZD, based on primary and secondary efficacy endpoints.
 
To assess the proportion of patients who suffer relapse within 12 months post randomization, out of those patients completing 16 weeks of therapy and achieving sustained sputum culture conversion, defined as two successive negative liquid media cultures at or before WK08, with no positives to follow until the week 16 visit.
 
Pharmacokinetics Objectives:
 
								
	Primary Priarmacokinetics Objective:								
	To describe the pharmacokinetics (PK) of DZD through development of a population PK model								

	Secondary Pharmacokinetics Objective:
	• To describe the PK of BDQ, DLM and MXF including their main metabolites
	Mycobacteriology Identification and Characterization Objectives:

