### 7 NON-IMP DRUGS USED IN THE STUDY

For clarity, all licenced drugs in this study (all drugs other than DZD), are referred to as 'non-IMP study drugs'. BDQ, DLM and MXF are meant by this term. When reference is made to 'study drugs' all drugs including DZD are meant.

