#### **Physical examination**

Details about the conduct of physical examination will be laid out in the Manual of Procedures (MOP)

- Weight (kg)/height (m)
- Physical examination
- Additionally, the Hunter criteria for early detection of serotonin syndrome will be assessed:
  - Spontaneous clonus
  - Inducible clonus
  - Ocular clonus
  - o Tremor
  - Hyperreflexia
  - o Agitation
  - Diaphoresis
  - Hyperthermia above 38ºC

Serotonin syndrome is diagnosed according to the following decision rule, which will prompt stopping a subject from receiving study drug if fulfilled. The Hunter Serotonin Toxicity Criteria are fulfilled if any of the following is fulfilled:

- Spontaneous clonus
- Inducible clonus PLUS agitation or diaphoresis
- Ocular clonus PLUS agitation or diaphoresis

- o Tremor PLUS hyperreflexia
- Hypertonia PLUS temperature above 38°C PLUS ocular clonus or inducible clonus

In the case of presence of newly appearing symptoms "inducible clonus", "ocular clonus", or "tremor", which would not fulfil Hunter criteria on their own, close observation of the participant (ideally daily) is warranted while continuing on medication, and the sponsor medical expert should be notified.

- Vital signs (temperature (degrees Celsius), blood pressure (systolic and diastolic, in mmHg), pulse (bpm), pulse oxymetry, and respiratory rate (breaths/minute)). Measurements for blood pressure and pulse rate will be performed in the supine position after at least 10 minutes rest using an oscillometric method. As far as possible, measurement will always be performed on the same arm.
- On visits WK00 and WK02, additional blood pressure measurements will be performed: WK00: after 1h, 2h and 3h (± 10 mins) after IMP is taken; WK02: 1h, 2h, 3h, 4h, 6h (± 10 mins) after intake of IMP

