# 12.2 Study drug dosage and administration

The experimental and control treatment as described above will be administered daily for 16 weeks (see Table 1. Daily Dosing of Study Medication), together with food.

- Bedaquiline: will be dosed as per the licensed dose: 400 mg orally once daily for the first 14 days, then 200 mg three times a week.
- Delamanid: will be dosed as per the licensed dose: 200 mg orally in two daily doses of 100 mg.
- Moxifloxacin: will be dosed as per the licensed dose: 400 mg orally once daily
- Delpazolid not licensed:
  - Dose: will be according to randomization to dosing arm:
    - Arm 1: 15 participants will receive 0 mg of DZD
    - Arm 2: 15 participants will receive 400 mg DZD orally once daily
    - Arm 3: 15 participants will receive 800 mg DZD orally once daily
    - Arm 4: 15 participants will receive 1200 mg DZD orally once daily
    - Arm 5: 15 participants will receive 800 mg DZD orally twice daily

The daily dose of study drug for participants will be dependent on the subjects' experimental arm as shown in the following table:

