## 14.2 Clarifications and exceptions

Occurrences will be registered as AE from administration of the first dose of study drugs. All events that occur or are elicited before administering any study drugs, e.g. screening laboratory abnormalities qualifying as Adverse Events, will be recorded as medical history. If such events meet criteria for seriousness, they will nevertheless be reported as SAEs.

Abnormalities which are not clinically significant as per the qualified judgement of the investigator do not constitute adverse events and are not recorded and reported as such. However, these abnormalities may be analysed and reported in the study report.

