#### 15.3.2 Adverse Events

The incidence of treatment – emergent adverse events, defined as all AEs that occur after the administration of IMP, and their relatedness to experimental treatment will be summarised by treatment group, by system organ class and preferred term, maximum severity, and potential relationship to IMP, as well as TEAEs with an outcome of death, serious TEAEs, and discontinuations due to TEAEs.

Adverse events will be coded using the Medical Dictionary for Regulatory Activities (MedDRA) dictionary.

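### Treatment-emergent AEs are counted from intake of the IMP, which Arm 1 never takes, so on the protocol's own terms the on-treatment TEAE summaries show a structural zero in the comparator

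*SAP*

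**What the plan says.** **The TEAE rule.** SAP 13.1.2 plans "The incidence of treatment-emergent adverse events, defined as all AEs that occur after the administration of IMP". Protocol 15.3.2 has the same anchor: "defined as all AEs that occur after the administration of IMP". Both summarise these events by treatment group, covering organ class and preferred term, maximum severity, relationship, serious events, deaths and discontinuations. The SAP limits these tables to onset within treatment or the following 14 days, and adds separate tables for the whole study period.

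**What IMP means.** The protocol synopsis names the IMP as "Delpazolid (DZD) 400 mg tablets". Protocol section 7 says that "all licenced drugs in this study (all drugs other than DZD), are referred to as 'non-IMP study drugs", lists bedaquiline, delamanid and moxifloxacin under that label, and keeps study drugs as the wider term that includes delpazolid.

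**What Arm 1 receives.** Protocol 12.2 states: "Arm 1: 15 participants will receive 0 mg of DZD". Table 1 of the protocol lists no delpazolid or placebo tablet for that arm.

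**Other anchors in the same documents.** Protocol 14.2: "Occurrences will be registered as AE from administration of the first dose of study drugs". The safety population (protocol 15.2.3, SAP 6.4) is everyone who received any study medication.

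**Extra blood pressure and heart rate readings.** The Schedule of Events (footnote F) and protocol 10.5.2 and 11.3 time these from the IMP. Section 11.3 has "WK00: after 1h, 2h and 3h (± 10 mins) after IMP is taken", and at week 2 five times, again counted from IMP intake.

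**The concern.** The safety objective (protocol 8.1, SAP 3.1) is to describe delpazolid plus the background regimen against the background regimen alone. Arm 1 is the only arm that supplies that second term. If treatment-emergence starts with a drug that Arm 1 never takes, the start date does not exist for that arm, and a program written to the definition returns no treatment-emergent events there.

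A zero in that column would not look like a gap. It would look like a clean control arm beside four arms with ordinary AE counts, and every between-arm contrast in those tables would overstate what delpazolid adds. The background drugs have AEs of their own, and separating those from delpazolid's is the reason for having the arm.

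The tables concerned are the ones restricted to the treatment period. The whole-study tables are a poorer substitute for an on-treatment comparison: they run to week 52 and so include events during the standard TB treatment given after week 16 to participants who did not meet the culture conversion rule.

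**Working it through.** The plan states no figure on this point, so the check is to trace the terms and then count.

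1. **Is IMP a defined term or shorthand for the regimen?** It is defined: the synopsis and section 7 restrict it to delpazolid. The distinction is also used in practice, since protocol 14.7 and 14.8 record action taken and causality separately for IMP and non-IMP study drugs. The SAP lists IMP only as an abbreviation and says that it is to be read with the protocol, so the protocol's meaning carries over.

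2. **Who has an IMP start?**
   - Participants: 5 arms × 15 = 75, which agrees with the stated total.
   - With at least one planned IMP dose: 4 × 15 = 60.
   - With none: 75 − 60 = 15, all in Arm 1; 15/75 = 20%.

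3. **What do the TEAE tables show for Arm 1?** The denominator is the safety population, which needs only some study medication, so Arm 1 contributes its 15. The numerator needs onset after an IMP dose that never occurs, so it is 0. The result is 0/15 for any true AE rate.

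4. **Do the other rules agree with this anchor?**

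| Rule | Time zero or entry condition | Arm 1 covered? |
|---|---|---|
| TEAE definition (protocol 15.3.2, SAP 13.1.2) | Administration of IMP | No |
| AE registration (protocol 14.2) | First dose of study drugs | Yes |
| AE recording (protocol 14.8) | Signed consent | Yes |
| Safety population (protocol 15.2.3, SAP 6.4) | Any study medication | Yes |

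The TEAE definition is the only one of the four that leaves Arm 1 out.

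5. **Which outputs still show Arm 1?** The whole-study AE tables in SAP 13.1.2 do. So do table shells 3.4.1 to 3.4.6, which cover all AEs, adverse reactions and serious events, have an Arm 1 column and are not limited to TEAEs. Shell 1.2 has a row for early discontinuation because of an adverse event.

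6. **After the change.** With the first dose of any study drug as the start, participants with a defined start go from 60/75 to 75/75.

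7. **Blood pressure and heart rate readings.** There are 3 at week 0 and 5 at week 2, so 8 per participant. In the text all are timed from IMP intake, and no section gives Arm 1 another reference. However, the schedule exempts no arm. Protocol 10.5.2 also puts examinations and laboratory samples for all participants before intake of IMP, and then describes the same laboratory sampling as preceding study treatment. At week 2 every participant has intensive PK sampling, and protocol 11.5 has the exact dosing time recorded as hour 0 that day, so a usable clock time exists in Arm 1 for 5 of the 8 readings.

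**The case against.** The strongest reply is that the intent is plain and the damage small. The same SAP paragraph reports by treatment group and uses a window around treatment, which Arm 1 does have. Protocol 10.5.2 shows IMP used loosely for the day's dose. Arm 1 AEs are collected under either start rule, its participants are in the safety population, and the AE shells that will be programmed are not restricted to TEAEs. A sensible programmer would produce sound tables.

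Most of this stands. It rules out any claim that Arm 1's AE data are lost or that the AE reporting as a whole has an empty comparator column. It does not rescue the definition. The protocol took care to separate IMP from study drugs, the same wording appears in both documents, and a pre-specified rule should not depend on someone overriding its text. Protocol 15.3.2 plans only TEAE summaries, and the treatment-plus-14-days tables are where the on-treatment comparison is made.

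On blood pressure, a reader might infer that Arm 1 would have no post-dose readings at all. The documents do not support that. No arm is exempted, all arms take study drugs in the morning, and the week 2 dosing time is recorded for everyone. The SAP's vital-sign shells tabulate by visit only, so no between-arm table of the post-dose series is planned that could lose its control. What remains is an unstated reference time.

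**Conclusion.** The TEAE definition is wrong as written. Read with the protocol's own terms, it gives 0/15 in the only comparator for every summary restricted to treatment-emergent events, against the safety objective and against the study-drug anchors used elsewhere. It affects 15 of 75 participants (20%) and one family of tables. The whole-study tables and the all-AE and SAE shells are unaffected.

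This rests on two assumptions: that IMP carries its defined meaning, and that the definition is programmed literally. If the programmer reads IMP as the regimen, the tables come out right but no longer follow the stated plan.

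Two further inferences are not drawn. The AE rates of the combination study in protocol 7.4 should not be used to say how many Arm 1 events would be hidden: its moxifloxacin arm also contained pyrazinamide, which Arm 1 does not receive. Nor is a significance test between arms at issue, because the planned safety analysis is descriptive.

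The blood pressure and heart rate timing is a secondary clarification. The Arm 1 time zero is undefined in the text, and nothing shows that readings would be missing.

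**What to change.** **TEAE definition.** In protocol 15.3.2 and SAP 13.1.2, define treatment-emergent as onset on or after the first dose of any study drug (delpazolid, bedaquiline, delamanid or moxifloxacin), in all five arms. Keep the SAP's 14-day post-treatment window. This is one phrase in each document, uses a term the protocol already defines, needs no new data and changes nothing in the delpazolid arms if all drugs start on the same day.

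**Timing of the extra readings.** In Schedule of Events footnote F and protocol 10.5.2 and 11.3, state that the week 0 and week 2 blood pressure and heart rate readings are timed from the morning study-drug intake in all arms. If the readings have already been taken, record in the SAP which reference time was used in Arm 1. This is also wording only; the readings are already in the common visit schedule.

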13.1.3. Prior and Concomitant Medication

Prior and concomitant medications will be summarized and listed on a per-participant basis, if a patient reported the same medication repeatedly, the medication will be counted only once in tables; counts (N) and percentages (%) will be presented by treatment arm. Concomitant medication will also be listed with one row for each occurrence of each medication per participant. If a medication has a completely missing or partially missing start/stop date, the date will be imputed as described above and then it will be classified as prior, concomitant, or post-treatment medication.

Imputation rules for missing or partial medication start/stop dates are defined above.

13.2. Method for safety analysis

Binary and categorical variables will be tabulated by treatment arm. Continuous variables will be summarized with location (such as mean or median) and precision (such as standard error or interquartile range) summary estimates.

Participants with worsening condition from baseline on any variable will be described and tabulated.

The following variables will be analyzed:

Participants with worsening condition from baseline on any variable will be described and tabulated. The following variables will be analyzed:

- Laboratory Parameters: a list of safety laboratory parameters collected in the trial is described under 'Safety Laboratory' in
- Ophthalmologic Variables: Visual Acuity (Snellen) and Colour Vision (Ishihara) tests
- Physical Examination incl. neurological examination; esp. presence of Hunter score criteria
- Vital signs Timings of Analyses
- Extent of exposure to all drugs

13.3. Interim Analyses for Data Safety Management Board (DSMB)

An independent data safety monitoring board (DSMB) will be convened for the trial. The DSMB will review safety data at regular intervals as defined in the DSMB Charter, DSMBs report will be provided including safety data. The sponsor and the medical monitor will remain blind to results, only the DSMB committee members and unblinded statistician(s) will see aggregate data by study arm.

13.4. Interim 16-week analysis

Analysis for the primary endpoints, and secondary endpoints unrelated to disease recurrence or relapse, will be performed after data are available (allowing for time for culture growth) after the last patient completed their WK16 (or otherwise last treatment) visit. This will be considered the primary analysis data extract for presentation and publications. Secondary outcomes including data after 16 weeks will be presented based on available data, recognizing that full data on these endpoints will not be available until the final analysis.

The sponsor and study staff will not remain blinded once this interim analysis has been undertaken.

A partial database lock will be performed for this purpose, with a final database lock at the end of study after all long-term outcome data are available.

13.5. Final Analysis

Analysis for the secondary and additional endpoints that include any data available after 16 weeks will be performed when the final database lock at the end of study after all long-term outcome data are available and all participant visits have been completed.

14. Further Analysis Details

Appendix: Shells of tables and listings

This section presents the shells for the planned Tables and Listings to be programmed in support of the planned analyses identified in the SAP. This section is intended to support the SAP and provides guidance on the programming specifications (shells) for the planned outputs and may be updated, with any updates appropriately documented, reviewed, and approved.

1. Demographic and Baseline

Table 1.1 Participant Disposition - All Participants Screened

	Arm 1 D0 (N=x) n (%)	Arm 2 D400 (N=x) n (%)	Arm 3 D800-OD (N=x) n (%)	Arm 4 D1200 (N=x) n (%)	Arm 5 D800-BD (N=x) n (%)	Total (N=x) n (%)
Screened for Eligibility						x
Randomized	xx (xx.x %)	xx (xx.x %)	xx (xx.x %)	xx (xx.x %)	xx (xx.x %)	xx (xx.x %)
Screen Failure [1]						x
Reason 1						x
Reason 2						x
Reason 3						x
Others						x

^[1] Participants who have not met eligibility criteria, or otherwise chose not to participate in the study.

Table 1.2 Participant Disposition - All Participants Randomized

	Arm 1 D0 (N=x) n (%)	Arm 2 D400 (N=x) n (%)	Arm 3 D800-OD (N=x) n (%)	Arm 4 D1200 (N=x) n (%)	Arm 5 D800-BD (N=x) n (%)	Total (N=x) n (%)
Randomized	xx (xx.x %)	xx (xx.x %)	xx (xx.x %)	xx (xx.x %)	xx (xx.x %)	xx (xx.x %)
Intent-To- Treat Population [2]	xx (xx.x %)	xx (xx.x %)	xx (xx.x %)	xx (xx.x %)	xx (xx.x %)	xx (xx.x %)
Adequate adherence (AA) population	xx (xx.x %)	xx (xx.x %)	xx (xx.x %)	xx (xx.x %)	xx (xx.x %)	xx (xx.x %)
Safety Population	xx (xx.x %)	xx (xx.x %)	xx (xx.x %)	xx (xx.x %)	xx (xx.x %)	xx (xx.x %)
Completed Study	xx (xx.x %)	xx (xx.x %)	xx (xx.x %)	xx (xx.x %)	xx (xx.x %)	xx (xx.x %)
Discontinued Early	xx (xx.x %)	xx (xx.x %)	xx (xx.x %)	xx (xx.x %)	xx (xx.x %)	xx (xx.x %)
Adverse Event	xx (xx.x %)	xx (xx.x %)	xx (xx.x %)	xx (xx.x %)	xx (xx.x %)	xx (xx.x %)
Subject Withdrawal of Consent	xx (xx.x %)	xx (xx.x %)	xx (xx.x %)	xx (xx.x %)	xx (xx.x %)	xx (xx.x %)

^[2] The ITT population will consist of all randomized participants in the groups to which they were randomly assigned, and who have taken at least one dose of study treatment.

v1.0, February 13, 2023

Table 1.3 Major Protocol Deviations Intent-To-Treat Population

Major Protocol Deviation Category	Arm 1 D0 (N=x) n (%)	Arm 2 D400 (N=x) n (%)	Arm 3 D800-OD (N=x) n (%)	Arm 4 D1200 (N=x) n (%)	Arm 5 D800-BD (N=x) n (%)	Total (N=x) n (%)
Participants with any Major Deviation	xx (xx.x %)	xx (xx.x %)	xx (xx.x %)	xx (xx.x %)	xx (xx.x %)	xx (xx.x %)
<deviation 1=""></deviation>	xx (xx.x %)	xx (xx.x %)	xx (xx.x %)	xx (xx.x %)	xx (xx.x %)	xx (xx.x %)
<deviation 2=""></deviation>	xx (xx.x %)	xx (xx.x %)	xx (xx.x %)	xx (xx.x %)	xx (xx.x %)	xx (xx.x %)
<deviation 3=""></deviation>	xx (xx.x %)	xx (xx.x %)	xx (xx.x %)	xx (xx.x %)	xx (xx.x %)	xx (xx.x %)

v1.0, February 13, 2023

Table 1.4 Demographic and Baseline Characteristics by Treatment Arm*

	Arm 1 D0 (N=x)	Arm 2 D400 (N=x)	Arm 3 D800-OD (N=x)	Arm 4 D1200 (N=x)	Arm 5 D800-BD (N=x)	Total (N=x) n (%)
	n (%)	n (%)	n (%)	n (%)	n (%)	
Sex, n (%)						
Female	xx (xx.x %)	xx (xx.x %)	xx (xx.x %)	xx (xx.x %)	xx (xx.x %)	xx (xx.x %)
Male	xx (xx.x %)	xx (xx.x %)	xx (xx.x %)	xx (xx.x %)	xx (xx.x %)	xx (xx.x %)
Age (years)						
Mean (SD)	xx	xx	xx	xx	xx	xx
Median	xx	xx	xx	xx	xx	xx
Min – Max	(xx, xx)	(xx, xx)	(xx, xx)	(xx, xx)	(xx, xx)	(xx, xx)
Race, n (%)						
Black	xx (xx.x %)	xx (xx.x %)	xx (xx.x %)	xx (xx.x %)	xx (xx.x %)	xx (xx.x %)
White	xx (xx.x %)	xx (xx.x %)	xx (xx.x %)	xx (xx.x %)	xx (xx.x %)	xx (xx.x %)
Asian	xx (xx.x %)	xx (xx.x %)	xx (xx.x %)	xx (xx.x %)	xx (xx.x %)	xx (xx.x %)
American Indian or Alaska Native	xx (xx.x %)	xx (xx.x %)	xx (xx.x %)	xx (xx.x %)	xx (xx.x %)	xx (xx.x %)
Other	xx (xx.x %)	xx (xx.x %)	xx (xx.x %)	xx (xx.x %)	xx (xx.x %)	xx (xx.x %)
Unknown	xx (xx.x %)	xx (xx.x %)	xx (xx.x %)	xx (xx.x %)	xx (xx.x %)	xx (xx.x %)
Ethnicity, n (%)						
Hispanic or Latino	xx (xx.x %)	xx (xx.x %)	xx (xx.x %)	xx (xx.x %)	xx (xx.x %)	xx (xx.x %)
Not Hispanic or Latino	xx (xx.x %)	xx (xx.x %)	xx (xx.x %)	xx (xx.x %)	xx (xx.x %)	xx (xx.x %)
Unknown	xx (xx.x %)	xx (xx.x %)	xx (xx.x %)	xx (xx.x %)	xx (xx.x %)	xx (xx.x %)
Height (cm)						
Mean (SD)	xx	xx	xx	xx	xx	xx
Median	xx	xx	xx	xx	xx	xx
Min – Max	(xx, xx)	(xx, xx)	(xx, xx)	(xx, xx)	(xx, xx)	(xx, xx)
Weigh (kg)						
Mean (SD)	xx	xx	xx	xx	xx	xx

Median	xx	xx	xx	xx	xx	xx
Min – Max	(xx, xx)					
BMI (kg/m²)						
Mean (SD)	xx	xx	xx	xx	xx	xx
Median	xx	xx	xx	xx	xx	xx
Min – Max	(xx, xx)					
HIV Status						
Positive	xx (xx.x %)					
Negative	xx (xx.x %)					
TTP at baseline (Median)						
Smear Grade baseline	xx	xx	xx	xx	xx	xx
Bacterial Load in Sputum (GeneExpert)						
≥16	xx (xx.x %)					
< 16	xx (xx.x %)					
Tobacco Use	xx (xx.x %)					
Number of Products Consumed	xx (xx.x %)					
Frequency	xx	xx	xx	xx	xx	xx
Alcohol Use	xx (xx.x %)					
Number of Products Consumed	xx (xx.x %)					
Frequency	xx	xx	xx	xx	xx	xx
Recreational drug use	xx (xx.x %)					
Number of Products Consumed	xx (xx.x %)					
Frequency	xx	xx	xx	xx	xx	xx

^{*} This table will be repeated for the mITT, AA, and safety population.

Table 1.5 Summary of Prior Medications by Treatment Arm

Prior Medications	Arm 1 D0 (N=x)	Arm 2 D400 (N=x)	Arm 3 D800-OD (N=x)	Arm 4 D1200 (N=x)	Arm 5 D800-BD (N=x)	Total (N=x) n (%)
	n (%)	n (%)	n (%)	n (%)	n (%)	11 (70)
<medication 1=""></medication>	xx (xx.x %)	xx (xx.x %)	xx (xx.x %)	xx (xx.x %)	xx (xx.x %)	xx (xx.x %)
<medication 2=""></medication>	xx (xx.x %)	xx (xx.x %)	xx (xx.x %)	xx (xx.x %)	xx (xx.x %)	(xx.x %)

PanACEA - DECODE - 01

<medication 3=""></medication>	xx (xx.x %)	(xx.x %)				
<medication< td="">xx (xx.x %)	xx (xx.x %)	xx (xx.x %)	xx (xx.x %)	xx (xx.x %)	XX	</medication<>	xx (xx.x %)	XX				
4>						(xx.x %)

Listing 1.1 Summary of Medical History by Subject

Subject ID	Condition	Start Date	End Date	Severity	Ongoing	Pattern of Condition
xxxxxx	X	x		x	x	x
xxxxxx	х	х		x	х	х
xxxxxx	x	х		х	х	х

Table 1.6 Summary of Baseline Culture Results by Randomized Treatment.

	Arm 1 D0 (N=x) n (%)	Arm 2 D400 (N=x) n (%)	Arm 3 D800-OD (N=x) n (%)	Arm 4 D1200 (N=x) n (%)	Arm 5 D800-BD (N=x) n (%)	Total (N=x) n (%)
Positive for MTB Complex	xx (xx.x %)	xx (xx.x %)	xx (xx.x %)	xx (xx.x %)	xx (xx.x %)	xx (xx.x %)
Positive for MTB Complex with contamination	xx (xx.x %)	xx (xx.x %)	xx (xx.x %)	xx (xx.x %)	xx (xx.x %)	xx (xx.x %)
Negative	xx (xx.x %)	xx (xx.x %)	xx (xx.x %)	xx (xx.x %)	xx (xx.x %)	xx (xx.x %)
Contaminated	xx (xx.x %)	xx (xx.x %)	xx (xx.x %)	xx (xx.x %)	xx (xx.x %)	xx (xx.x %)
No Results	xx (xx.x %)	xx (xx.x %)	xx (xx.x %)	xx (xx.x %)	xx (xx.x %)	(xx.x %)

2. Analysis of Efficacy
<Describe the efficacy analysis and results>

Table 2.1 Summary of Culture Results by Randomized Treatment of Week 00.

	Arm 1 D0 (N=x) n (%)	Arm 2 D400 (N=x) n (%)	Arm 3 D800-OD (N=x) n (%)	Arm 4 D1200 (N=x) n (%)	Arm 5 D800-BD (N=x) n (%)	Total (N=x) n (%)
Positive for MTB Complex	xx (xx.x %)	xx (xx.x %)	xx (xx.x %)	xx (xx.x %)	xx (xx.x %)	xx (xx.x %)
Positive for MTB Complex with contamination	xx (xx.x %)	xx (xx.x %)	xx (xx.x %)	xx (xx.x %)	xx (xx.x %)	xx (xx.x %)
Negative	xx (xx.x %)	xx (xx.x %)	xx (xx.x %)	xx (xx.x %)	xx (xx.x %)	xx (xx.x %)

PanACEA - DECODE - 01

| Contaminated | xx (xx.x %) | xx
(xx.x %) |
|--------------|-------------|-------------|-------------|-------------|-------------|----------------|
| No Results | xx (xx.x %) | xx
(xx.x %) |

Table 2.2 Summary of Culture Results by Randomized Treatment of Week 02.

{Similar shell table as Table 2.1}

Table 2.3 Summary of Culture Results by Randomized Treatment of Week 08.

{Similar shell table as Table 2.1}

Table 2.4 Summary of Culture Results by Randomized Treatment of Week 12.

{Similar shell table as Table 2.1}

Table 2.5 Summary of Culture Results by Randomized Treatment of Week 14.

{Similar shell table as Table 2.1}

Table 2.6 Summary of Culture Results by Randomized Treatment of Week 16.

{Similar shell table as Table 2.1}

Table 2.7 Summary of Time to Positivity (TTP) by Treatment Arm of Week 00*.

TTP	Arm 1 D0 (N=x) n (%)	Arm 2 D400 (N=x) n (%)	Arm 3 D800-OD (N=x) n (%)	Arm 4 D1200 (N=x) n (%)	Arm 5 D800-BD (N=x) n (%)	Total (N=x) n (%)
Mean (SD)	xx	xx	xx	xx	xx	xx
Median	xx	xx	xx	xx	xx	xx
Min – Max	(xx, xx)	(xx, xx)	(xx, xx)	(xx, xx)	(xx, xx)	(xx, xx)

^{*}Same tables will be applied to each week (from week 00 to week 16).

Table 2.8 Analysis of Time to Culture Conversion on Liquid Media.

TTP	Arm 1 D0 (N=x) n (%)	Arm 2 D400 (N=x) n (%)	Arm 3 D800-OD (N=x) n (%)	Arm 4 D1200 (N=x) n (%)	Arm 5 D800-BD (N=x) n (%)
25th centile, weeks	xx	xx	xx	xx	xx
Median (50th centile), weeks	xx	xx	xx	xx	xx
75th centile, weeks	xx	xx	xx	xx	xx
Mean	xx	xx	xx	xx	xx

v1.0, February 13, 2023

% With culture conversion at 0 week					
% With culture conversion at 2 weeks	xx.x%	xx.x%	xx.x%	xx.x%	xx.x%
% With culture conversion at 4 weeks	xx.x%	xx.x%	xx.x%	xx.x%	xx.x%
% With culture conversion at 6 weeks	xx.x%	xx.x%	xx.x%	xx.x%	xx.x%
% With culture conversion at 8 weeks	xx.x%	xx.x%	xx.x%	xx.x%	xx.x%
% With culture conversion at 12 weeks	xx.x%	xx.x%	xx.x%	xx.x%	xx.x%
% With culture conversion at 14 weeks	xx.x%	xx.x%	xx.x%	xx.x%	xx.x%
% With culture conversion at 16 weeks	xx.x%	xx.x%	xx.x%	xx.x%	xx.x%
Unadjusted Hazard Ratio (95% CI)	1	xx(xx, xx)	xx(xx, xx)	xx(xx, xx)	xx(xx, xx)
Adjusted Hazard Ratio (95% CI)*	1	xx(xx, xx)	xx(xx, xx)	xx(xx, xx)	xx(xx, xx)

^{*} Analysis has been adjusted for: gender, age, race, BMI, HIV status, baseline culture (using time to positivity)

Table 2.9 Analysis of Time to Culture Conversion on Solid Media.

TTP	Arm 1 D0 (N=x) n (%)	Arm 2 D400 (N=x) n (%)	Arm 3 D800-OD (N=x) n (%)	Arm 4 D1200 (N=x) n (%)	Arm 5 D800-BD (N=x) n (%)
25th centile	xx	xx	xx	xx	xx
Median (50th centile)	xx	xx	xx	xx	xx
75th centile	xx	xx	xx	xx	xx
% With culture conversion at 0 week	xx.x%	xx.x%	xx.x%	xx.x%	xx.x%
% With culture conversion at 8 weeks	xx.x%	xx.x%	xx.x%	xx.x%	xx.x%
% With culture conversion at 12 weeks	xx.x%	xx.x%	xx.x%	xx.x%	xx.x%

% With culture conversion at 14 weeks	xx.x%	xx.x%	xx.x%	xx.x%	xx.x%
% With culture conversion at 16 weeks	xx.x%	xx.x%	xx.x%	xx.x%	xx.x%
Hazard Ratio (95% CI)	xx (xx, xx)				

 $Figure\ 2.1:\ Kaplan-Meier\ plot\ of\ time\ to\ first\ of\ two\ negative\ culture\ conversions.$

{including Kaplan - Meier plot comparing 4 arms with number at risk/control below}

Table 2.10 Summary of Relapse by Treatment Arm

Total in ITT analysis population	Arm 1 D0 (N=x) n (%)	Arm 2 D400 (N=x) n (%)	Arm 3 D800-OD (N=x) n (%)	Arm 4 D1200 (N=x) n (%)	Arm 5 D800-BD (N=x) n (%)	Total (N=x) n (%)
Not achieved time to stable culture conversion	xx (xx.x %)	xx (xx.x %)	xx (xx.x %)	xx (xx.x %)	xx (xx.x %)	xx (xx.x %)
Relapse	xx (xx.x %)	xx (xx.x %)	xx (xx.x %)	xx (xx.x %)	xx (xx.x %)	xx (xx.x %)
Time to relapse (mean +- SD)	xx (xx)	xx (xx)	xx (xx)	xx (xx)	xx (xx)	xx (xx)
Reinfection	xx (xx.x %)	xx (xx.x %)	xx (xx.x %)	xx (xx.x %)	xx (xx.x %)	xx (xx.x %)
Time to Reinfection (mean +- SD)	xx (xx)	xx (xx)	xx (xx)	xx (xx)	xx (xx)	xx (xx)
Death	xx (xx.x %)	xx (xx.x %)	xx (xx.x %)	xx (xx.x %)	xx (xx.x %)	xx (xx.x %)
Culture positive when last seen	xx (xx.x %)	xx (xx.x %)	xx (xx.x %)	xx (xx.x %)	xx (xx.x %)	xx (xx.x %)
Culture negative when last seen	xx (xx.x %)	xx (xx.x %)	xx (xx.x %)	xx (xx.x %)	xx (xx.x %)	(xx.x %)

Table 2.11 Summary of Drug resistance by Treatment and Visit:

Arm 1 D0 (N=x)	Arm 2 D400 (N=x)	Arm 3 D800-OD (N=x)	Arm 4 D1200 (N=x)	Arm 5 D800-BD (N=x)	Total (N=x)
----------------------	------------------------	---------------------------	-------------------------	---------------------------	----------------

Number of			
Participants			
Drug Name			
of			
Resistance			
Proportion			
of			
Participants			
developing			
drug			
resistance			
among those			
not			
converting			
to negative			
culture.			

Listing 2.1 Listing of all Drug Resistance

{This section will list a record of all drug resistance, including drug name, visit number, participant ID etc. F}

{Additional sensitivity analysis will be performed with alternative definitions of time to culture conversion, tables 2.8 and 2.9 will be repeated for each sensitivity definition of time to culture conversion.}

3. Safety Evaluation

